Uncontrolled hypertension (>160/90).

Hypotension (systolic < 90).

Uncontrolled seizures.

Planned initiation of chemotherapy, radiotherapy or bisphosphonates within 30 days prior to treatment with study drug.

Received an investigational drug within 30 days prior to study.

History of allergy to lidocaine or other topical, local or infusional anesthetics.

Methods

Recruitment

Subjects will be recruited from the BCCA Pain and Symptom Management/ Palliative Care (PSMPC) clinics at 5 sites - Vancouver, Kelowna, Abbotsford, Centre for the North and Fraser Valley. All patients attending BCCA PSMPC clinics complete a detailed pain and symptom and palliative care assessment. This includes worst pain intensity over the last 3 days as well as pain impact on function, and a body map to indicate location of pain. All patients attending the PSMPC clinics at the Vancouver and Kelowna Centres will be screened for eligibility by the research nurse and attending physician and then approached either by the attending physician or the clinic nurse as to whether or not they would like to hear about the study. If they would, the physician or research nurse will give the subject the consent form. The subject will be given the opportunity to thoroughly review and ask any questions they may have. Potential subjects from the Abbotsford and Fraser Valley sites will be approached by a Pain and Symptom Management/Palliative Care Team physician or nurse at those sites and referred to Vancouver for completion of study procedures, including consent and treatment. Once the consent is signed blood will be drawn for creatinine/GFR, bilirubin level, electrolytes if not already done in the 30 days prior to recruitment.

Baseline Visit

The baseline visit will include: documenting of age, gender, weight, history and physical, cancer diagnosis, (PPS), Edmonton Classification System for Cancer Pain (ECS-CP), medication and allergy history, blood pressure, pulse rate and ECG result, and physician assessment of cause(s) of pain(s). Patients will complete BPI, POS questionnaires and will be given a Medication Use Log to record their pain medication use for 3 days prior to their treatment day. Subjects will be introduced to the Brief Pain Inventory (BPI) at this time. This is a widely accepted and validated pain

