Subjects will be monitored for pre infusion vital signs and then clinically for the 1st hour, with vital signs (blood pressure, pulse oximetry, pulse rate) measured every 15 minutes, and physician to be contacted if the vital signs fall outside of the defined parameters. The infusor will be inspected every 15 minutes during this first hour to ensure that it appears to be emptying at the expected rate. Adverse events will be documented. After the 1st hour, if stable, subjects will be allowed to leave the clinic with their caregiver but will be required to stay within 30 mins from the cancer centre and to return for infusor inspection and vital signs measuring halfway through the infusion (+/- 30 mins) and again within 1 hour of completion of the infusion (total 5.5 hours). They will be required to have a cell phone (one will be provided if they do not already have one) in order to be able to contact the study nurse/physician if they experience any adverse effects, and be able to return for assessment quickly. A patient lounge area will be available at the cancer centre if the patient wishes to stay in the building. Subjects will be provided with the telephone numbers for the study nurse and the physician. A physician will be at the cancer centre throughout all infusions and in the event of a serious adverse reaction will assess the patient immediately. Subjects and companions will be reimbursed reasonable expenses for lunch and parking at the Cancer Centre if needed.

Regular opioid dosing during the treatment day will be determined by discussion with the study nurse/physician, considering the subjects' pain levels. If the subject is responding sufficiently that sedation could result from relief of pain, the subject will be instructed by the nurse/physician to reduce their regular opioid dose. The magnitude of dose reduction will be individually determined according to pain levels and any sedation experienced.

Blood will be drawn for lidocaine level during the hour before the infusion is completed, and the infusor removed once empty (approximately 5.5 hours post)End of infusion outcomes, including BPI, POS, Medication Use Log and Adverse Events Log, vital signs will be collected and the patient will resume their normal or reduced dose of opioid at the time of their next scheduled dose, reduced as needed.

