Prior to the First Scheduled Treatment:

Medication Use Log use for three days prior to the first treatment visit

Day 1 pre each infusion:

BPI, POS, and Medication Use Log, review of Adverse Events Log, vital signs, attach Holter Monitor. The Holter Monitor will record for the duration of each infusion plus 4 hours subsequently, and will be removed by the patient.

During each infusion:

Vital signs will be measured and the infusor will be inspected every 15 minutes for the 1st hour, halfway through the infusion and on completion; the physician will be contacted ASAP if the pulse drops to less than 60 beats per minute or increases to over 100 beats per minute, or the PaO₂ falls below 90%; systolic BP changes by 25mm from pre-treatment BP. Patients will be given a Medicaton Log and an Adverse Event Log to keep track of any A/Es they experience.

In the hour prior to completion of each infusion (i.e. 4.5 to 5.5 hours since started: no later than between 2.00 and 3.00pm):

A lidocaine blood level will be drawn at the appropriate BCCA laboratory and the subject's vital signs will be taken. Blood will be analysed at the Provincial Toxicology Lab, Vancouver

At the end of each infusion on Day 1:

BPI, POS, Medication Use Log, assessment of toxicity via Adverse Events Log and vital signs.

At each of the intervals where the vital signs are to be taken, the patient's pain score will be assessed and recorded and the infusion site will be assessed to ensure the medication is infusing properly

Daily During Study:

Medication Use Log

Subjects encouraged to call study physician if any concerns
On day 2 and 3 after each Infusion and at least twice a week
or until pain is back to pre-treatment level

Phone call by physician or study nurse to review opioid dosing, adverse events and subject's perception of pain relief

Once pain returned to baseline, once weekly telephone contact will be done til the 2nd treatment visit to review any condition or medication changes

At 10.00am on Day 2 and Day 3 post each infusion, BPI and POS Questionnaires to be completed.

If there is a response to the treatment, the patient will also complete them on Day, 7, 14 and 21, or until the worst pain score on the BPI #3 has returned to baseline . If there is not a response , the BPI and POS Questionnaires will only be required for Day 2, 3 and 7.

Daily

Medication Use Log to be completed and Adverse Events Log if subject experiences symptoms or side-effects

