The assumptions of no carry-over effect, no period effect and no sequence effect are made under this study. To check these assumptions, a repeated measures logistic regression model will be fitted to model the probability of pain reduction by treatment type (placebo versus lidocaine), stratifying by the treatment order (first or second treatment). This model accounts for inter-subject variation and within-subject correlation. Score tests will be used to test whether the treatment order estimate equals to zero at a 5% significance level. Rejection of this null hypothesis implies a carry-over effect, period effect and sequence effect.

Safety Considerations:

Any subject with unrecognized allergy to lidocaine would be expected to react within the first hour, and subjects will be closely observed during that

time. Any later side-effect will be able to be addressed promptly by the patient returning to the Cancer Centre for assessment by the nurse and/or physician. There is an emergency response team in the cancer centre during working hours and the study physician will be available for the duration of all infusions.

References:

1. Bartlett EE and Hutaserani O. Xylocaine for the relief of postoperative pain. *Anesth Analg* 1961; 40:296-304.
2. Edmondson EA et al. Systemic lidocaine therapy for post-stroke pain. *Southern Medical Journal* Oct 1993 86(10):1093-1096
5. Strichartz G. Protracted Relief of Experimental Neuropathic Pain by Systemic Local Anesthetics: How, Where, and When. *Anesthesiology*: Volume 83(4) October 1995 pp 654-655.

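### The only blood-pressure trigger for calling the physician during infusion is a 25 mm systolic change; a floor at the plan's own hypotension limit of 90 should be added

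*Combined protocol and SAP*

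**What the plan says.** The First Treatment Day section requires vital signs every 15 minutes in the first hour, "and physician to be contacted if the vital signs fall outside of the defined parameters". The parameters are defined in only one place, Schedule of Assessments, During each infusion. There the physician is to be contacted:

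- "if the pulse drops to less than 60 beats per minute or increases to over 100 beats per minute";
- if oxygen falls below 90%;
- if "systolic BP changes by 25mm from pre-treatment BP".

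Pulse and oxygen have absolute limits. Systolic pressure has only a change from the starting value.

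The exclusion criteria list "Hypotension (systolic < 90" as a reason not to enrol. They give no date for the check, and no other section turns the limit into a call limit during the infusion.

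First Treatment Day also says: "After the 1st hour, if stable, subjects will be allowed to leave the clinic with their caregiver". No number is attached to stable. The patient is then "to return for infusor inspection and vital signs measuring halfway through the infusion (+/- 30 mins" either side, and again within an hour of completion. As cover, "A physician will be at the cancer centre throughout all infusions", and under Safety Considerations "There is an emergency response team in the cancer centre during working hours".

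**The concern.** The plan treats a systolic pressure below 90 as reason enough to withhold the drug. Once the drug is running, the written call rule can be silent in that same state, because it looks only at the size of the change. It is weakest where reserve is smallest: a fall from 140 to 115 calls the physician, while a fall from 90 to 66 does not.

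This is a question of patient safety. The readings are recorded whether or not anyone is called, and the primary endpoint, the alpha and the power do not depend on the rule. A call that would be wanted may be missed or delayed. That matters most at the one-hour point, when a patient may leave the clinic with the infusion still running.

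**Working it through.** The plan gives no figure on this point to reproduce, so the check is direct arithmetic on the rule as written.

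**Inputs**

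- Trigger: a systolic change of 25 mm from pre-treatment (Schedule of Assessments, During each infusion). I read this as 25 or more, in whole mmHg, so changes of up to 24 are silent.
- Hypotension limit: systolic below 90 (Exclusion criteria).
- Infusion length 5.5 h; possible release after 1 h; mid-infusion reading at halfway, with 30 minutes' tolerance (First Treatment Day).

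**Lowest silent reading.** For a starting systolic S, the lowest reading with no blood-pressure call is S − 24. A fall that ends below 90 must be at least S − 89, so the silent falls into hypotension run from S − 89 to 24.

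| Start S | Lowest silent reading (S − 24) | Silent falls ending below 90 |
|---|---|---|
| 90 | 66 | 1 to 24 |
| 100 | 76 | 11 to 24 |
| 110 | 86 | 21 to 24 |
| 113 | 89 | 24 only |
| 114 | 90 | none |

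The gap therefore covers starts of 90 to 113 and narrows as the start rises. If the exclusion is not rechecked on the treatment day and a patient starts below 90, it is wider: from 85 the lowest silent reading is 85 − 24 = 61.

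**Time to the next reading after release.** Halfway is 5.5 / 2 = 2.75 h. With 0.5 h either way, the reading falls between 2.25 and 3.25 h. Release at 1 h leaves 2.25 − 1 = 1.25 h to 3.25 − 1 = 2.25 h before the next scheduled reading.

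**With a floor added.** If the rule becomes a call when the reading is below 90 or differs from S by 25 or more, the lowest silent reading is 90 for every start from 90 to 113, in place of 66 to 89. Nothing changes for starts of 114 or more.

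**Number of readings.** Four in the first hour, one halfway, one in the last hour and one at the end: 4 + 1 + 1 + 1 = 7 scheduled readings per infusion.

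**The case against.** The strongest reply is that this is a preference and not a defect. An eligibility limit and a call limit serve different purposes, and the plan never says that one must double as the other. That is right as far as it goes: there is no contradiction in the document. But the limit is the plan's own, and the call rule is silent in a state the plan treats as unsafe for dosing. It is also true that no ceiling is carried over from the hypertension exclusion: a start of 137 to 160 can read above 160 with no call (137 + 24 = 161). A missing ceiling does not justify a missing floor.

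Second, several safeguards overlap. For harm to follow, a nurse would have to read a systolic in the 60s to 80s, judge the patient stable and call no one, with a physician in the building. Patients must be able to report symptoms, and they have a caregiver and a phone. This stands as a reason to expect few events. The documents do not say how a nurse would judge such a reading, and the physician and emergency team help only once someone calls.

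Third, past experience is reassuring. Clinical Experience reports over 3000 subcutaneous infusions, without toxicity-related problems. Cardiovascular Monitoring cites a cancer-pain trial with no cardiovascular toxicity. This supports a low frequency, with limits. The subcutaneous experience was uncontrolled and at 1.5 mg/kg/h, against 10 / 5.5 = 1.8 mg/kg/h here. The cited trial gave 4 mg/kg intravenously and took blood pressure every 10 minutes.

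Fourth, the interval after release is not caused by the missing floor, and the floor does not shorten it. That is correct. The floor would, however, require a call for a first-hour reading already below 90, before the patient is allowed to leave.

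Finally, a floor might prompt interventions or stopped infusions in patients whose pressure is habitually low, and so feed the toxicity outcome. An intervention made because of a true systolic below 90 is toxicity the plan means to count.

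**Conclusion.** The concern holds as a modest safety improvement. It is not an error or a contradiction in the plan. Under the current rule any start from 90 to 113 permits a reading below the plan's own hypotension limit with no blood-pressure call, down to 66 at the extreme.

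This rests on reading the trigger as 25 or more. Confidence is high in the wording and the arithmetic. It does not extend to how often the situation would arise: the documents give neither the share of patients who start at 90 to 113 nor the distribution of falls, and the reported experience suggests few cases. The statistical design is unaffected.

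**What to change.** In Schedule of Assessments, During each infusion, replace the blood-pressure trigger with: *systolic pressure below 90 mmHg, or a change of 25 mmHg or more from the pre-treatment value*.

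As a secondary clarification, because the exclusion carries no date, state that the physician is contacted before the infusion starts if that day's pre-infusion systolic is below 90. That reading is already taken.

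**Cost.** One sentence and one clarification, with no new measurements.

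- The floor brings a few more calls to a physician already on site. For starts of 90 or more they arise only at 90 to 113. A patient who starts below 90 and is allowed to proceed would prompt a call at each reading still below 90, up to 7 per infusion.
- The pre-infusion clarification may occasionally postpone an infusion after the long-acting opioid has been omitted that morning or the fentanyl patch removed the night before (Baseline Visit). That patient would have had an unneeded opioid switch, and a prepared infusor might be wasted.

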This study's primary objective is to test the hypothesis that a single infusion of subcutaneous lidocaine can cause a clinically useful reduction in cancer pain within 48 hours of infusion and lasting a minimum of 7 days. A clinically useful reduction in pain is defined by either a 2-point reduction (on a 0-10 scale) in the worst pain experienced over a 24-hour period, or a $\geq 30\%$ reduction in 24-hour opioid requirement. We will use a composite endpoint of reduction in pain without increase in 24-hr opioid requirement or no decrease in pain with a $\geq 30\%$ reduction in 24-hour opioid requirement.

The secondary objectives are 1) to determine whether any significant toxicities occur as a result of the infusion. For this study significant toxicity is considered as any adverse event which either leads to the infusion being terminated, or which leads to medical intervention, such as prescribing of another medication or equivalent treatment, 2) to determine the effect of Lidocaine infusion on QOL parameters as measured by the Patient Outcome Scale (POS) Questionnaire and 3) to determine the duration of response to lidocaine infusion.

Eligibility criteria:

Male or female patients 18 years of age or older
In or outpatients referred to the BCCA PSMPC Clinics with a diagnosis of cancer
Subjects must have somatic, visceral or neuropathic pain related to cancer
Pain intensity, measured by a worst pain score over the last 72 hours of ≥ 4 on a 0-10 numerical rating scale
Must have tried at least one opioid medication without adequate response or with significant side-effects for at least one week
For those with neuropathic pain, must have also tried at least one adjuvant analgesic, such as a tricyclic (unless contraindicated) or an anticonvulsant without adequate response or with significant side-effects for at least one week
Life expectancy of > 3 months
Must be able to communicate symptoms indicating potential toxicity of Lidocaine
Must have a competent caregiver in the home overnight after each infusion
Must be willing to remain within 30 minutes of the Cancer Centre during each infusion

Exclusion criteria:

Clinically significant cardiac disease, i.e, cardiac failure, atrial fibrillation with slow ventricular rate (<60), any degree of heart block

New analgesic treatment initiated in time frame which might have effect within one week of study drug.

Hyper or hypokalemia.

Liver failure (bilirubin ≥ 25 μ mol/L).

Renal failure (eGFR <50% of normal)

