assessment tool which asks for pain severity over the 24 hours prior to completion, which makes it very suitable for repeated use in assessing response to lidocaine. It takes only a few minutes to complete. The pain assessment on the morning of the infusion will be the baseline point for determination of response in the study, but subjects will need to be familiar with it in order for repeated scoring throughout the study. Introducing the BPI at the baseline visit will allow it to be explained without the time pressure of needing to start the infusion.

At the baseline visit the subjects will be instructed as to discontinuation of their long-acting opioid on the morning of treatment as appropriate for the pharmacokinetics of the particular opioid: For those on Morphine, Oxycodone or Hydromorphone their long-acting dose will be omitted on the morning of the treatment, and the dose divided into three 4-hourly doses of the short-acting preparation of the same drug. In the absence of a response to treatment, the long-acting dose will be re-assessed at the end of the treatment day. If the subject does experience analgesia from the study drug then the dosing of the long-acting opioid will be adjusted as needed according to that response by telephone advice from the study physician.

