After the baseline visit, subjects will be scheduled for their first treatment within 14 days, and instructions sent to pharmacy accordingly. On the day prior to first treatment the subject will be randomized according to a predetermined schedule held in the dispensing pharmacy in a double-blind fashion to either placebo (D5W) or active drug (10 mg/kg preservative-free lidocaine). Both products will be administered subcutaneously via a Baxter infusor. All infusions will be made up to the same volume with D5W by a licensed pharmacist. The infusors are designed to deliver the whole contents at a constant rate over 5.5 hours, so the actual dose rate will vary depending on the subject's body weight.

Prior to the First Scheduled Treatment:

Subjects will be asked to complete a Medication Use Log for three days prior to the first treatment visit

First Treatment Day

On the day of infusion any long-acting opioid medication will be switched to short-acting as described above, because a dramatic response to lidocaine could theoretically reduce pain such that symptoms of opioid toxicity such as sedation could arise if the opioid dose was large. If this does occur the short-acting opioid dose can be reduced. It should be noted that this problem has only been seen in in-patients on high dose opioids and has not been observed in our experience with intravenous lidocaine infusions in ambulatory patients.

Subjects will be met by the study nurse who will complete the Day 1 assessment, including the Brief Pain Inventory, POS and Medication Use Log and a Holter monitor will be attached by a cardiology technician. The preferred location of insertion of the subcutaneous catheter (usually the abdomen) will be injected with 1ml of 1% lidocaine subcutaneously at least 2 minutes before insertion of the subcutaneous catheter in order both that the catheter insertion will be painless, and also for blinding, as the lidocaine infusion will produce a degree of numbness in the area once the infusion is started, whereas the placebo infusion (D5W) will not. The amount of lidocaine in 1ml of 1% solution is only 10mg, and will not cause

any systemic analgesia. The infusion (lidocaine or D5W placebo) will start between 0900 - 0930hrs.

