At 1000 am on Day 2 and Day 3, the BPI and POS will be completed. If there is a reduction in pain scores, the BPI and POS will continue to be completed on Day 7, 14 and 21 post each infusion, or until the worst pain score on the BPI #3 has returned to baseline. If there is no change, the questionnaires for Day 7 will be completed and the patient will be scheduled for the next follow up visit and treatment within a minimum of 48 hours and maximum of three weeks of the pain returning to baseline. The Medication Use Log is to be completed daily, and the Adverse Events Log completed if an adverse event occurs. Telephone contact will be made at a minimum twice a week until the pain is back to the pre-treatment level by the research nurse or physician and to adjust medications if necessary, and, once pain returned to baseline, once weekly telephone contact will be done til the 2nd treatment visit to review any condition or medication changes. Subjects will also be encouraged to call the physician at any time if they experience any adverse event or to report return to baseline pain score.

Once the worst pain score on the BPI (question #3) has returned to baseline and at least 48 hours have elapsed, the second treatment will be arranged. If there is a response the patient will continue with diaries and questionnaires weekly until the BPI score returns to baseline

Second Treatment Visit

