This will be arranged within a minimum of 48 hours and maximum of three weeks of the pain returning to baseline but will be no earlier than 48 hours after the 1st treatment. The baseline weight will be used to determine the dose for the second treatment. At 1000 am on Day 2 and Day 3 post second treatment, the BPI and POS will be completed. If there is a reduction in pain scores, the BPI and POS will continue to be completed on Day 7, 14 and 21 post each infusion, or until the worst pain score on the BPI #3 has returned to baseline, at which time the end of study visit will be arranged within a minimum of 48 hours and a maximum of three weeks of the pain returning to baseline. If there is no change, the questionnaires for Day 7 will be completed and the patient will be scheduled for the end of study visit within a minimum of 48 hours and maximum of three weeks of the pain returning to baseline. The Medication Use Log is to be completed daily, and the Adverse Events Log completed if an adverse event occurs. Telephone contact will be made at a minimum twice a week until the pain is back to the pre-treatment level. Subjects will also be encouraged to call the physician at any time if they experience any adverse event or to report return to baseline pain score.

Final Visit Post Second Infusion (once the worst pain score on the BPI (question #3) has returned to baseline by phone assessment and at least 48 hours or a maximum of three weeks of the pain returning to baseline., At this visit subjects will again complete the Brief Pain Inventory and POS and their Medication Use Log and Adverse Events Log will be reviewed. This will be the end of the study.

Outcome measures:

Primary:

The primary outcomes measure is a binary variable indicating whether lidocaine caused a reduction in cancer pain within 48 hours of infusion and lasting a minimum of 7 days. Lidocaine will be considered to have caused reduction in cancer pain if the subject had either one of the following episodes lasting a minimum of 7 days:

- 1) A 2-point reduction in severity of pain as assessed by the worst pain score in the last 24 hours (question 3) of the Brief Pain Inventory – Short Form (BPI), compared to the BPI pain score at baseline.

Or:

- 2) ≥30% reduction in 24-hour opioid dose.

The duration of the pain reduction is measured by weekly BPI pain scores.,

Secondary:

- 1) Incidence and severity of adverse events.

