Final Visit: (post 2nd infusion, once the worst pain score on the BPI (question #3) has returned to baseline by phone assessment and minimum 48 hours and a maximum of three weeks since the return to baseline., At the final visit, the ,BPI, POS, Medication Use Log. Adverse Events Log and PPS will be reviewed

A positive response re: pain relief would be defined as any of the following:

- A 2-point reduction in worst pain intensity (#3 on the BPI) within 48 hours of infusion and lasting a minimum of 7 days
- Reduction in analgesic dose by greater or equal to 30% will also be considered an indicator of positive response.

Statistical Considerations: **Objective**

To compute the power and sample size calculation for the study

Assumptions

- Probability of response in the placebo group = 30%
- There is no carry-over effect, no period effect and no sequence effect in the study

- 0.01% of the patients who did not respond to the lidocaine will respond to the placebo

Null Hypothesis: There is no difference between a single infusion of subcutaneous lidocaine and the placebo

Alternative Hypothesis: A single infusion of subcutaneous lidocaine can cause a reduction in cancer pain

Sample Size / Interim Analysis

A sample size of 40 patients achieves 84% power to detect a 20% difference at a 2.5% significance level using a one-sided McNemar's Test, under the assumptions that 30% of the patients respond to the placebo and 0.01% of the patients who do not respond to the lidocaine will respond to the placebo. This sample size is increased to 50 patients to account for a 20% drop-out rate. This drop-out rate is based on our experience accruing similar patients to studies. The sample size methodology is based on the methodology described in Lachenbruch 1992.

We have demonstrated in the completed Feasibility Study for a Randomized Double Blind Placebo Controlled Crossover Trial of the Use of Subcutaneous Lidocaine Infusion for Chronic Cancer-related Pain that recruitment to such a study is feasible, and that we should expect this study to take 6 months for accrual.

An interim analysis will be carried out after 20 patients have completed the study to allow the trial to be stopped early for demonstrated efficacy. One-sided McNemar's tests will be carried out to test whether a single infusion of subcutaneous lidocaine will cause a reduction in cancer pain for both the interim and final analyses at the p-values of 0.00153 and 0.02347 respectively.

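### The primary endpoint has conflicting definitions and no opioid reference dose, so the same patient can be a responder or not depending on which section is applied

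*Combined protocol and SAP*

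**What the plan says.** **Study Objectives.** A clinically useful reduction is first given as either a 2-point fall in worst pain or an opioid fall of at least 30%. The next sentence then sets a conditional composite: "We will use a composite endpoint of reduction in pain without increase in 24-hr opioid requirement or no decrease in pain", the second arm being completed by a 24-hour opioid fall of at least 30%. The 48-hour onset and 7-day duration come from the objective itself.

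**Outcome measures, Primary.** The subject responds "if the subject had either one of the following episodes lasting a minimum of 7 days": a 2-point fall on BPI question 3 from baseline, or a fall of at least 30% in 24-hour opioid dose. Neither limb carries a condition on the other. The only duration measure given is "The duration of the pain reduction is measured by weekly BPI pain scores".

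**Positive-response definition, end of Schedule of Assessments.** The pain bullet has the 48 hours and 7 days. The opioid bullet has neither: "Reduction in analgesic dose by greater or equal to 30% will also be considered an indicator of positive response".

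**Reference values.** Baseline Visit fixes a baseline for pain: "The pain assessment on the morning of the infusion will be the baseline point for determination of response in the study". For opioid there is a log, "Subjects will be asked to complete a Medication Use Log for three days prior to the first treatment visit", which then runs daily and is reviewed on Day 1 before each infusion. It is never named as the comparator.

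**Release of the second infusion.** Between Visits arranges it "Once the worst pain score on the BPI (question #3) has returned to baseline and at least 48 hours have elapsed". Second Treatment Visit adds a floor of 48 hours after the first treatment. Neither section sets an opioid condition.

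**The concern.** The primary analysis is a McNemar test on a yes/no response in each period, so every patient has to be scored twice by a single rule. The plan offers several rules and does not say which governs. They differ in substance: whether pain relief counts when opioid use rises, whether an opioid cut counts when pain changes, and whether the cut must last.

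A 30% fall also cannot be scored without a denominator. If the reference for infusion 2 is left open, a reduction that followed infusion 1 can be credited to infusion 2 or not, as the analyst chooses. The patients for whom the opioid limb was written, who accept similar pain on less opioid, may already be at baseline pain and so eligible for the second infusion. What is at stake is a choice of definition or reference that might be made after the codes are known, in a trial where one patient can move the result across the threshold.

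**Working it through.** **1. The plan's own figure.** Inputs from Sample Size / Interim Analysis: N = 40, placebo response 30%, difference 20 points (so lidocaine 50%), 0.01% placebo response among lidocaine non-responders, one-sided 2.5%.
- Placebo-only probability = 0.0001 × 0.50 = 0.00005; lidocaine-only = 0.20 + 0.00005 = 0.20005.
- Exact one-sided McNemar power = 83.8%, the same at the final threshold of 0.02347. The stated 84% reproduces, and 40/(1 − 0.20) = 50. The sample-size calculation is not in question.

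**2. The definitions applied literally to four patients.** In the composite, reduction in pain is taken as the 2-point fall defined in the sentence before it.

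| Patient | Objectives composite | Primary outcome | Positive-response definition |
|---|---|---|---|
| Pain down 2 points for 7 days, opioid up | No | Yes | Yes |
| Pain down 1 point, opioid down 40%, 7 days | No | Yes | Yes |
| Pain unchanged, opioid down 30% for 3 days | No | No | Yes |
| Pain worse, opioid down 30% for 7 days | Yes | Yes | Yes |

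The first three rows are classified differently. In the fourth all three agree, but a patient in more pain counts as a success. The second patient would respond under the simpler sentence that precedes the composite, so Study Objectives is also inconsistent within itself.

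**3. Reference dose (illustration).** Opioid falls from 100 mg to 65 mg after infusion 1 and stays there.
- Infusion 2 against the log before infusion 1: (100 − 65)/100 = 35%, a response.
- Infusion 2 against the log before infusion 2: (65 − 65)/65 = 0%, no response.

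**4. Timing.** Count the infusion as Day 1. Onset within 48 hours means by Day 3, and 7 days from Day 3 run to Day 9. The earliest second infusion that cannot cut into the window is Day 10. The stated floor allows Day 3 if the pain score is at baseline.

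**5. What one patient is worth.** Exact one-sided McNemar p for b lidocaine-only and c placebo-only responders, against 0.02347:
- 5:0 gives 0.5^5 = 0.031 (not significant); 6:0 gives 0.5^6 = 0.0156 (significant).
- 7:1 gives 0.035; 8:1 gives 0.0195. One placebo-only responder raises the number needed from 6 to 8.

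**6. Noise from loose scoring (assumed rate).** Let a non-responding period be scored as a response with probability f, equal and independent in both periods. The documents give no value for f.
- Lidocaine-only = 0.20005(1 − f) + 0.49995·f(1 − f); placebo-only = 0.00005(1 − f) + 0.49995·f(1 − f).
- f = 5%: 0.2138 and 0.0238, power 64%. f = 10%: 0.2250 and 0.0450, power 50%.

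The loss is steep because the plan assumes almost no placebo-only responders.

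**The case against.** **The dosing rules already prevent most of this.** Between Visits lets long-acting opioid be reduced only when the patient feels pain control has improved enough, and returns patients to their prior regimen once the effect wears off. Baseline Visit says, for fentanyl and methadone users, that patients without relief have no opioid reduction. Worse pain on less opioid, or a cut that outlasts the return of pain, should therefore be uncommon. This stands as a limit on frequency. These are rules for prescribing, though, and do not say how to score a patient.

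**Day 7 is expected for everyone.** The schedule asks for questionnaires on Days 2, 3 and 7 even without a response, so re-infusion on Day 3 is not what the plan has in view. This largely stands, but Day 7 does not guarantee 7 full days of opioid data when onset is on Day 2 or 3, and the 48-hour floor remains in the text. Nor is every opioid-only responder at baseline pain: under the primary outcome a patient with a 1-point fall and a 30% cut is not. The gap concerns only those whose pain score is at baseline.

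**The Primary heading governs, and the later bullet is a summary.** That is a reasonable reading, but the later list says it defines a positive response, and the conflict between Study Objectives and the primary outcome would remain.

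**A stronger inference to resist.** First Treatment Day has staff instruct opioid cuts sized partly by sedation, and the background lists sedation as mild lidocaine toxicity. A reader might infer that such cuts would be scored as lidocaine benefit and inflate the false-positive rate. The documents do not support that. Staff are blinded, the trigger is perceived relief (which the plan's 30% placebo response allows for), slow infusions are said to give levels free of toxicity, and the 7-day rule screens out a cut confined to the infusion day. If such cuts are scored equally often in both periods, at 2.5% to 10%, with independent periods and no drug effect, the false-positive rate stays at about 1.2% to 1.3%. The planned split of the morning dose, "the dose divided into three 4-hourly doses of the short-acting preparation of the same drug", is a substitution and not a cut.

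**Conclusion.** The concern holds as an inconsistency in the primary endpoint and a missing reference dose. It should be corrected before unblinding. Neither part rests on an assumed frequency: the definitions classify the same patient differently, and a 30% opioid fall cannot be scored as written. The release rule for the second infusion adds a narrower gap for opioid-only responders whose pain is at baseline.

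The size is set by how little separates success from failure: 6 against 5 lidocaine-only responders when none are reversed. Some fragility is common to any binary endpoint at this sample size; what is avoidable here is leaving the classification open. How many patients would be affected cannot be read from the documents, and the dosing rules suggest few. With blinding intact, the expected effect of infusion-day cuts scored as response is noise and lost power (84% to 64% at an assumed 5% in each period), not a clear advantage for lidocaine.

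**What to change.** Before unblinding:

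1. Use one definition in Study Objectives, Outcome measures and the positive-response definition, and delete the separate opioid bullet in the last. Response is either:
   - (i) a fall of 2 points or more on BPI question 3 from that infusion's morning baseline, within 48 hours and lasting 7 days, with 24-hour opioid (oral morphine equivalent) not above the reference; or
   - (ii) mean 24-hour oral morphine equivalent over 7 days, starting within 48 hours, at least 30% below the reference, with worst pain not above that infusion's baseline on Days 2, 3 and 7.
2. Define the reference as the mean of the 3 Medication Use Log days before that infusion, and require the log for those 3 days before each infusion. Using a 7-day mean in (ii) avoids failing a patient for one bad breakthrough day.
3. Do not give the second infusion until the 7-day window is complete and both BPI question 3 and 24-hour opioid dose have returned to baseline.
4. Add a supporting McNemar test on the pain limb alone, and list opioid-only responders by treatment.

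**Cost.** Mainly wording, since the log is already kept daily. Slightly fewer opioid-only responders: power is about 80% if the 20-point difference becomes 19, and 75% at 18. The pain-only test has less power (57% if pain alone carries 15 of the 20 points), so it should stay supporting. Some second infusions move a few days later, to Day 10 when onset is on Day 3, and patients with a lasting opioid reduction wait longer, as lasting pain responders already do. Opioid reductions needed for safety remain allowed at any time.
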